6.3.1 Outcome variables

Effectiveness outcome variables of interest (definitions provided in **Appendix A**):

• **Primary outcome:** Changes in HbA1c from baseline to 26 weeks of treatment (end of follow-up).

Note. In the trial, HbA1c was also measured at 8, 12, 18 weeks (± 3 days) after randomization. Missing values of HbA1c at 26 weeks were replaced using last observation carried forward (LOCF) in the intention-to-treat (ITT) analysis set. In the replication, HbA1c at baseline will be defined as the last recorded HbA1c value measured within 90 days before and including cohort entry date in both groups. HbA1c at the end of follow-up will be defined as a recorded HbA1c value closest to the end of the 26th week and measured between 56 and 212 days (8-30 weeks) after cohort entry.

Secondary outcome: --

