6.3.2 Primary analysis and study follow-up

As-treated (AT) analysis will be performed as main analysis. The treatment drug will be defined as the index drug assigned on the day of cohort entry. Patients will be followed for about 30 weeks (212 days). Compared to the trial (Nauck M et al. 2009), we will

extend the follow-up and the outcome assessment periods of 4 weeks. The follow-up and outcome assessment window will start 56 days after cohort entry date and will continue until the earliest date of the following events:

- The first occurrence of the outcome of interest (measured between 56 and 212 days after cohort entry),
- The date of end of continuous registration in the database (disenrollment or end of available data),
- End of the study period,
- Measured death event occurs,
- Index drugs discontinuation (liraglutide, glimepiride or metformin),
- Crossover or addition of drug from the other treatment group,
- Addition of any other anti-diabetic medications,
- Nursing home admission
 - Nursing home admissions are considered a censoring event because the data sources utilized typically provide little to no data on a patient, particularly on drug utilization, after admission. We will utilize this as an exclusion reason for cohorts for the same reason.

Note. To decrease the incidence of missing values of the outcome (specifically, missing of HbA1c values measured between 56-212 days after cohort entry), we required that the eligible patients had at least 3 HbA1c measurements recorded within 365 days before and including cohort entry. This will increase the probability of including in the final cohort patients who are adherent to a routinely HbA1c testing and, consequently, will decrease the frequency of missing values of the outcome. Multiple imputation will be used to handle missing values in the primary analysis, while complete case analysis will be applied in a sensitivity analysis.

7. Initial Feasibility Analysis

Aetion report name:

For liraglutide vs. glimepiride

Optum CDM (continuous HbA1c outcome) https://bwh-dope.aetion.com/projects/details/1688/rwrs/71723

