Non-zero median value [IQR]	7.00 [6.60, 7.70]

^{*} patients who were censored between cohort entry and the beginning of the outcome assessment window/follow-up (i.e., 0.5-56 days after cohort entry) will not contribute to the unmatched and matched cohorts.

• Report median follow-up time by treatment group For liraglutide vs. glimepiride

Median Follow-Up Time (Days) [IQR] – AT analysis		
Patient Group Optum CDM		
Overall Patient Population	99 [84, 148]	
Referent	101 [84, 148]	
Exposure	88 [79, 130]	

• Report reasons for censoring in the overall study population

• For liraglutide vs. glimepiride

	Overall (n. 3,470)	Liraglutide (n. 378)	Glimepiride (n. 3,092)
Outcome *	2,262 (65.2%)	233 (61.6%)	2,029 (65.6%)
Death	2 (0.1%)	0 (0%)	2 (0.1%)
Start of an additional exposure	8 (0.2%)	3 (0.8%)	5 (0.2%)
End of index exposure	368 (10.6%)	74 (19.6%)	294 (9.5%)
Maximum follow-up time	336 (9.7%)	22 (5.8%)	314 (10.2%)
End of patient data	37 (1.0%)	3 (0.8%)	34 (1.1%)
End of patient enrollment	108 (3.1%)	12 (3.2%)	96 (3.1%)
Start of additional antidiabetic drugs + Nursing home + Metformin discontinuation with allowed 60 days gap	349 (10.1%)	22 (5.82%)	314 (10.2%)

^{*} patients with outcome recorded between 56-212 days after cohort entry.

• Report overall mean (sd) of the primary outcome.

	Optum CDM
Outcome – Lab value HbA1cmean (sd)	7.24 (1.01)

8. Initial Power Assessment

Analysis report name:

For liraglutide vs. glimepiride

Optum CDM – see file LEAD-2_programming_steps and output of "STEP 2 - INITIAL POWER Assessment - PS matching on age, gender, CCI (with dummy outcome) - Paragraphs 8 of the protocol"

Date conducted: 06/16/2021

In order to complete the initial power analysis, the dummy outcome of a 90-day gap in database enrollment will be used. This outcome is used to ensure that no information on the comparative risks of the outcomes of interest are available at this stage.

Complete a 1:1 PS-matched comparative analysis using this outcome. PS should include only 3 covariates: age, gender and combined comorbidity index. Power calculations are based on the formulas from Julios et al. (2008).

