Patient Group	Overall (n. 746)	Liraglutide (n. 373)	Glimepiride (n. 373)
Overall Patient Population	188 [97 - 212]	150 [89 - 212]	212 [119 -212]

• Report overall mean (sd) of the primary outcome (from initial feasibility analysis).

	Optum CDM
Outcome – Lab value HbA1cmean (sd)	7.24 (1.01)

10. Final Power Assessment

Date conducted:

• Re-calculate power in the appropriate excel table, using the revised number of matched patients from the PS-match in Section 9. All other parameters in the table should be the same as in Section 8.

Non-inferiority Analysis	
Standard deviation of outcome	1.01
Non-inferiority limit	0.4
Alpha (2-sided)	0.05
Power (1-beta)	90%
Sample size required per group	110
Total sample size required	220
Number of patients matched	746
Reference	373
Exposed	373

• Stop analyses until balance and final power assessment are reviewed by primary investigators, FDA, and assigned members of advisory board.

Reviewed by PI:	[name]	Date reviewed:	07/16/2021
Reviewed by FDA:	[name]	Date reviewed:	08/2/2021
Reasons for stopping			
analysis (if required):			

11. Study Confidence and Concerns

Deadline for voting on study confidence and listing concerns:

Date votes and concerns are summarized:

- If final feasibility and power analyses are reviewed and approved, proceed to the remaining protocol steps.
- All study team and advisory board members that review this protocol should at this stage provide their level of confidence for the success of the RWD study in the Google Form. This form also provides space for reviewers to list any concerns that they feel may

contribute to a failure to replicate the findings of the RCT, including differences in study populations, poor measurement of study variables, or residual confounding. All responses will be kept confidential and individual-level results will only be shared with the individual respondent.

• After the deadline for voting has passed, provide the distribution of responses and summarize all concerns here.

12. Register study protocol on clinicalTrials.gov

Date conducted:

• Register the study on clinicalTrials.gov and upload this document.

13. Comparative Analyses

Aetion report name:

Date conducted:

- 13.1 For primary analysis:
- 13.2 For sensitivity analyses:

14. Requested Results

14.1 Table 1: Baseline characteristics before and after adjustment

Variable	Before adjustment		After adjustment			
	Referent	Exposure	Std. diff.	Referent	Exposure	Std. diff.

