	Exposure: Liraglutide s.c. 0.6 mg/day, 1.2 mg/day and 1.8 mg/day in combination with metformin (1500-2000 mg/day) for 26 weeks Reference for non-inferiority: Glimepiride (4 mg/day) in combination with metformin (1500-2000 mg/day) Reference for superiority: Metformin monotherapy (1500-2000 mg/day) Aim: To evaluate whether the effect on glycaemic control (as measured by change in HbA1c) of treatment with 0.6 mg/day, 1.2 mg/day and 1.8 mg/day of liraglutide in combination with metformin was superior to metformin monotherapy and non-inferior to metformin and glimepiride combination therapy after 26 weeks of treatment.	Exposure: new-use of Liraglutide (washout 180 days) in combination with metformin NDC Generic Name: LIRAGLUTIDE NDC Brand name: Viktoza (FlexPen) Reference: new use of Glimepiride (washout 180 days) in combination with metformin NDC Generic Name: GLIMEPIRIDE NDC Brand name: GLIMEPIRIDE AMARYL		Criteria
	PRIMA	RY OUTCOME		Adequate mapping in claims
	Change in HbA1c from baseline to week 26 Note: in the trial missing values are replaced with last value carried forward [LVCF]	Measured as change in HbA1c from baseline to the last recorded HbA1c value between 56 and 212 days after drug initiation: Loinc codes: 17855-8, 17856-6, 41995-2, 43150-2, 4548-4, 4549-2, 55454-3, 71875-9, 74246-0		Intermediate mapping in claims
	INCLUS	SION CRITERIA		Poor mapping or cannot be measured in claims
0	Informed consent obtained before any trial-related activities (trial-related activities are any procedure that would not have been performed during normal management of the subject).	N/A		Can't be measured in claims but not important for the analysis
1	(1.1) Subjects diagnosed with type 2 diabetes and (1.2) treated with OAD(s) for at least three months.	1.1 Selecting patients with a diagnosis of type 2 diabetes measured from the time of enrollment to the day of drug initiation inpatient (any position), outpatient (any position): Type 2 diabetes: 1.1 Selecting patients with at least two prescriptions of metformin within 183 days before cohort entry (OADs treatment ≥ 3 months), and 1.3 Concomitant or current use of metformin at cohort entry date in both treatment groups: Generic name: Metformin Hel 1.4 Selecting patients with no other anti-diabetic treatments within the 180 days before cohort entry:		

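### One HbA1c from days 56-212 stands for the week-26 outcome, no stated analysis accounts for its day, and as-treated censoring probably makes it earlier on liraglutide

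*Combined protocol and SAP*

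**What the plan says.** Section 6.3.1 defines the primary outcome as "Changes in HbA1c from baseline to 26 weeks of treatment (end of follow-up". The final value is the one "closest to the end of the 26th week and measured between 56 and 212 days (8-30 weeks) after cohort entry".

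Two other places give a different selection rule. Section 6.3.2 ends follow-up at "The first occurrence of the outcome of interest (measured between 56 and 212 days after cohort entry". The primary-outcome row of Appendix A uses the "last recorded HbA1c value between 56 and 212 days after drug initiation".

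The main analysis is as-treated. Follow-up also ends at discontinuation of the index drug or metformin, crossover, addition of another antidiabetic drug, disenrolment, death or nursing home admission. Missing outcomes are multiply imputed, with complete case as the sensitivity analysis, but the imputation model is not described. Sections 13.1 and 13.2 are empty, and the results shell in Section 14.4 is laid out for hazard ratios.

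Of the trial, Section 6.3.1 says: "In the trial, HbA1c was also measured at 8, 12, 18 weeks (± 3 days) after randomization". It continues: "Missing values of HbA1c at 26 weeks were replaced using last observation carried forward (LOCF) in the intention-to-treat (ITT) analysis set".

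**The concern.** The target is a contrast at one time point, but the measurement may come from any point in a 22-week window. A value from day 56 and one from day 182 enter the analysis alike. HbA1c responds gradually, so an early value shows only part of the eventual change.

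Two consequences follow. If one arm is measured earlier, its change is understated relative to the other. If both arms are measured well before week 26, the study estimates an average over weeks 8-30 and then compares it with a week-26 trial estimate and the margin set for it. Settling the first, closest or last question does not remove either consequence, because as-treated censoring limits which values exist under every rule.

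**Working it through.** **1. On-treatment follow-up when HbA1c does not end it (Section 9, matched, dummy outcome).** The row reads "Overall Patient Population 188 [97 - 212] 150 [89 - 212] 212 [119 -212" (overall, liraglutide, glimepiride). The printed percentages in the censoring table use 746 as denominator; on 373 per arm they become:
- Reached day 212: liraglutide 137/373 = 36.7%; glimepiride 203/373 = 54.4%.
- Ended index exposure: 137/373 = 36.7%; 57/373 = 15.3%.

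Week 26 is day 182. With a median of 150 days, at least half of the liraglutide arm ends follow-up 182 - 150 = 32 days or more before week 26. No selection rule can give those patients an on-treatment value at day 182. At least half of the glimepiride arm is followed to day 212.

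**2. When outcomes occurred in the feasibility run (Section 7, unmatched).** Median follow-up is 88 days [79, 130] for liraglutide and 101 [84, 148] for glimepiride, that is weeks 12.6 and 14.4. Overall it is 99 [84, 148], against 188 in the matched dummy-outcome run, so this run appears to stop at the first HbA1c. These medians mix patients who had an HbA1c with patients censored without one, but a bound on the outcomes alone is available:
- Upper quartile 148, so at most 25% of 3,470 = 868 patients have follow-up beyond day 148.
- 336 of those reached maximum follow-up without an outcome.
- At most 868 - 336 = 532 of 2,262 outcomes (23.5%) fall after day 148, so at least 76% were taken by day 148, which is 34 days before week 26.

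*Assumption:* days are counted from cohort entry. Section 9's maximum of 212 implies this for that table. The liraglutide lower quartiles support it for Section 7: counted from day 56, 79 would mean day 79 + 56 = 135, later than the 89 in the dummy-outcome run on nearly the same patients (373 of 378), although stopping at an HbA1c can only shorten follow-up.

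**3. Size of a between-arm shift.** The documents give no time course. Assume both drugs approach a 1.0-point fall (the trial estimate in Section 1.6) as f(t) = 1 - 0.5^(t/h), with half-life h = 21, 28 or 35 days, and treat the follow-up medians as if they were measurement days:
- Day 88: 0.945, 0.887, 0.825. Day 101: 0.964, 0.918, 0.865. Difference 0.019, 0.031, 0.040.
- Day 150 versus day 212: difference 0.006, 0.019, 0.036.

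The shift is about 0.01-0.04 points, or 1.5% (0.006/0.4) to 10% (0.040/0.4) of the margin. Liraglutide looks slightly worse. With a much slower course (time constant 90 days, scaled to 1.0 at day 182) the two differences would be 0.06 and 0.11.

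**4. Distance from week 26 within each arm.** Under the same model, day 182 gives 0.998, 0.989, 0.973. A day-88 value falls short by 0.053, 0.102, 0.148; a day-101 value by 0.034, 0.071, 0.108. At each half-life, each shortfall exceeds the gap between arms. It cancels in the contrast only so far as the two drugs share a time course, on which the documents are silent.

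**5. Is power an obstacle to a stricter definition?** The plan's 110 per group reproduces at one-sided 0.05: 2 × 1.01² × (1.645 + 1.282)² / 0.4² = 109.2, rounded up to 110. At the labelled two-sided 0.05 it is 2 × 1.01² × (1.960 + 1.282)² / 0.4² = 134. Applying the liraglutide feasibility proportion to the matched arm gives 373 × 233/378 = 230 observed outcomes. Power at two-sided 0.05 is then Φ(0.4 / (1.01 × √(2/230)) - 1.96) = Φ(2.29) = 98.9%.

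**The case against.** - **Timing is already the selection criterion.** A reader might infer that any HbA1c counts, with no regard to when it was taken. Section 6.3.1 does not support that: it picks the value nearest week 26. What stands is that the rule chooses only among the values a patient has, and nothing later in the plan uses the day.
- **Unequal measurement times are inferred.** This stands. HbA1c day by arm is reported nowhere. The follow-up medians include patients censored without a value, who are imputed rather than measured early, and the Section 7 interquartile ranges overlap heavily. However, an imputation model built on undated, mostly early values would carry the same mixture forward.
- **The size is easily exaggerated.** Under the assumed half-lives, a day-56 value differs from a day-182 value by 0.16-0.30 points, which looks like 39-76% of the margin. That is one patient's gap, whereas the margin applies to a difference in means. The arm-level figure is the relevant one.
- **The direction does not favour liraglutide.** A reader might infer that early measurement helps the non-inferiority claim. The shift that can be quantified runs against liraglutide. Shrinkage toward zero needs a true difference to shrink, and the trial estimate is 0.0.
- **The trial was not purely week 26 either.** It carried earlier visits forward, so its estimate may include earlier values. There, though, this was the repair for missing values within scheduled visits; here an off-time value is part of the primary definition.
- **A baseline up to 90 days old does not add to the imbalance.** It stretches the interval behind a change to 212 + 90 = 302 days, but the rule is the same in both arms and time on treatment stays at 56-212 days.
- **Silence is not exclusion.** Section 13 is empty and the imputation model unspecified, so timing might yet be handled. That is a reason to write it down now.

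**Conclusion.** The concern holds in moderate form. As written, the plan estimates a mixture of week 8-30 effects, probably earlier on liraglutide, and sets it against a week-26 trial estimate and its 0.4 margin. The matched follow-up of 150 versus 212 days shows that this persists under the first, closest or last rule.

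The likely between-arm shift is small: about 0.01-0.04 points against liraglutide, at most about 10% of the margin. This rests on an assumed common exponential course, a 3-5 week half-life, a 1.0-point effect, and follow-up medians standing in for unreported measurement days. The departure from week 26 in both arms is the larger matter. Its effect on the contrast cannot be sized from the documents, because it depends on whether the two drugs act at different speeds.

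A reader might infer that the non-inferiority conclusion is seriously biased, or that the primary analysis must become a repeated-measures model. The documents support neither. Such a model is one option among several.

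**What to change.** 1. Reconcile the three selection rules in Sections 6.3.1, 6.3.2 and Appendix A, and use one throughout.
2. Report the distribution of HbA1c day by arm among patients with an observed outcome, separately from follow-up time.
3. In the multiple imputation already planned, make week 26 (a stated window around day 182) the target, and use dated earlier on-treatment HbA1c values as predictors instead of substituting them for it. At a minimum, add this as a sensitivity analysis.
4. Add a sensitivity analysis limited to values near week 26, for example weeks 18-30.

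**Cost.** SAP wording and modest programming to retain every dated HbA1c in the window, since a run that stops at the first value would not hold them all. More week-26 values would be imputed, more of them on liraglutide, so the confidence interval widens. The result would also lean on the assumption that, given baseline and earlier values, censored patients would have followed the course of those who stayed on treatment; state that assumption. Power is not at risk in the main analysis (about 99% with some 230 observed per arm, using the plan's SD of 1.01). The narrower-window subset will be smaller, and its size cannot be read from the documents.

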6.3.2 Primary analysis and study follow-up

As-treated (AT) analysis will be performed as main analysis. The treatment drug will be defined as the index drug assigned on the day of cohort entry. Patients will be followed for about 30 weeks (212 days). Compared to the trial (Nauck M et al. 2009), we will

extend the follow-up and the outcome assessment periods of 4 weeks. The follow-up and outcome assessment window will start 56 days after cohort entry date and will continue until the earliest date of the following events:

- The first occurrence of the outcome of interest (measured between 56 and 212 days after cohort entry),
- The date of end of continuous registration in the database (disenrollment or end of available data),
- End of the study period,
- Measured death event occurs,
- Index drugs discontinuation (liraglutide, glimepiride or metformin),
- Crossover or addition of drug from the other treatment group,
- Addition of any other anti-diabetic medications,
- Nursing home admission
 - Nursing home admissions are considered a censoring event because the data sources utilized typically provide little to no data on a patient, particularly on drug utilization, after admission. We will utilize this as an exclusion reason for cohorts for the same reason.

Note. To decrease the incidence of missing values of the outcome (specifically, missing of HbA1c values measured between 56-212 days after cohort entry), we required that the eligible patients had at least 3 HbA1c measurements recorded within 365 days before and including cohort entry. This will increase the probability of including in the final cohort patients who are adherent to a routinely HbA1c testing and, consequently, will decrease the frequency of missing values of the outcome. Multiple imputation will be used to handle missing values in the primary analysis, while complete case analysis will be applied in a sensitivity analysis.

7. Initial Feasibility Analysis

Aetion report name:

For liraglutide vs. glimepiride

Optum CDM (continuous HbA1c outcome) https://bwh-dope.aetion.com/projects/details/1688/rwrs/71723

Optum CDM (binary HbA1c outcome [flag: presence or absence of an HbA1c result within 56-212 days after cohort entry]) – calculated merging the databases from $\frac{https://bwh-dope.aetion.com/projects/details/1688/rwrs/71715}{https://bwh-dope.aetion.com/projects/details/1688/rwrs/71715}$ and $\frac{https://bwh-dope.aetion.com/projects/details/1688/rwrs/71715}{https://bwh-dope.aetion.com/projects/details/1688/rwrs/71715}$

dope.aetion.com/projects/details/1688/rwrs/71716 – see file LEAD-2_programming_steps and output of "STEP 1 - Initial FEASIBILITY Analysis (with study outcome) - Paragraph 7 of the protocol"

Date conducted: 06/17/2021

Complete Aetion feasibility analysis using age and CCI as the only covariates and the primary endpoint (Section 6.3.1) as the outcome. No measures of association will be computed nor will mean and standard deviation of the HbA1c outcome stratified by treatment group.

• Report patient characteristics by treatment group For liraglutide vs. glimepiride

	Optum CDM		
	Glimepiride - Comparator	Liraglutide - Exposure	Difference
Number of patients *	3,096	378	- (-, -)
Age			
mean (sd)	64.24 (10.37)	59.22 (10.94)	5.02 (3.90, 6.13)
median [IQR]	67.00 [58.00, 72.00]	60.00 [51.00, 68.00]	- (-, -)
Gender			
M = MALE; n (%)	1,726 (55.7%)	179 (47.4%)	8.39% (3.08%, 13.7%)
F = FEMALE; n (%)	1,370 (44.3%)	199 (52.6%)	-8.39% (-13.7%, -3.08%)
Combined Comorbidity Score - CCI (180 days)			
mean (sd)	2.06 (1.56)	1.86 (1.36)	0.19 (0.03, 0.36)
median [IQR]	2.00 [1.00, 3.00]	2.00 [1.00, 2.00]	- (-, -)

^{*} The overall n. of patients in the unmatched cohort is 3,470. Patients who were censored between cohort entry and the beginning of the outcome assessment window (n. 290 patients) are excluded from the Table reporting patient characteristics by groups because they will not contribute to the unmatched or matched cohorts.

• Report summary parameters of study population **FEASIBILITY- FOR STUDY OUTCOME For** liraglutide vs. glimepiride

	Optum CDM
Number of patients in full cohort	3,764
Number of patients that did not begin follow-up *	290
Number of patients	3,474
Number of person-years of patients that did begin the follow-up	1,118.53
Number of patients in group: Glimepiride	3,096
Number of patients in group: Liraglutide	378
Outcome - Lab value HbA1c	
mean (sd)	7.24 (1.01)
median [IQR]	7.00 [6.60, 7.70]
minimum	4.1
maximum	13.4
Number of patients with zero value	0
Non-zero mean value (SD)	7.24 (1.01)
Non-zero median value [IQR]	7.00 [6.60, 7.70]

^{*} patients who were censored between cohort entry and the beginning of the outcome assessment window/follow-up (i.e., 0.5-56 days after cohort entry) will not contribute to the unmatched and matched cohorts.

• Report median follow-up time by treatment group For liraglutide vs. glimepiride

Median Follow-Up Time (Days) [IQR] – AT analysis		
Patient Group Optum CDM		
Overall Patient Population	99 [84, 148]	
Referent	101 [84, 148]	
Exposure	88 [79, 130]	

• Report reasons for censoring in the overall study population

• For liraglutide vs. glimepiride

	Overall (n. 3,470)	Liraglutide (n. 378)	Glimepiride (n. 3,092)
Outcome *	2,262 (65.2%)	233 (61.6%)	2,029 (65.6%)
Death	2 (0.1%)	0 (0%)	2 (0.1%)
Start of an additional exposure	8 (0.2%)	3 (0.8%)	5 (0.2%)
End of index exposure	368 (10.6%)	74 (19.6%)	294 (9.5%)
Maximum follow-up time	336 (9.7%)	22 (5.8%)	314 (10.2%)
End of patient data	37 (1.0%)	3 (0.8%)	34 (1.1%)
End of patient enrollment	108 (3.1%)	12 (3.2%)	96 (3.1%)
Start of additional antidiabetic drugs + Nursing home + Metformin discontinuation with allowed 60 days gap	349 (10.1%)	22 (5.82%)	314 (10.2%)

^{*} patients with outcome recorded between 56-212 days after cohort entry.

• Report overall mean (sd) of the primary outcome.

	Optum CDM
Outcome – Lab value HbA1cmean (sd)	7.24 (1.01)

8. Initial Power Assessment

Analysis report name:

For liraglutide vs. glimepiride

Optum CDM – see file LEAD-2_programming_steps and output of "STEP 2 - INITIAL POWER Assessment - PS matching on age, gender, CCI (with dummy outcome) - Paragraphs 8 of the protocol"

Date conducted: 06/16/2021

In order to complete the initial power analysis, the dummy outcome of a 90-day gap in database enrollment will be used. This outcome is used to ensure that no information on the comparative risks of the outcomes of interest are available at this stage.

Complete a 1:1 PS-matched comparative analysis using this outcome. PS should include only 3 covariates: age, gender and combined comorbidity index. Power calculations are based on the formulas from Julios et al. (2008).

• Stop analyses until feasibility and power are reviewed by primary investigators and FDA. Reviewers evaluate the results of the analyses described above in Sections 7 and 8, including numbers of patients, patient characteristics, follow-up time, and reasons for censoring by treatment group, as well as overall rates of outcomes and study power. These parameters are re-evaluated and reported in the subsequent sections, after incorporating feedback and refining the protocol.

o Optum CDM

Non-inferiority Analysis	
Standard deviation of outcome	1.01
Non-inferiority limit	0.4
Alpha (2-sided)	0.05
Power (1-beta)	90%
Sample size required per group	110
Total sample size required	220
Number of patients matched	752
Reference	376
Exposed	376

• Stop analyses until feasibility and power are reviewed by primary investigators, FDA, and assigned members of advisory board.

Reviewed by PI:	[name]	Date reviewed:	07/16/2021
Reviewed by FDA:	[name]	Date reviewed:	08/2/2021
Reasons for stopping			
analysis (if required):			

9. Balance Assessment

For liraglutide vs. glimepiride

Optum CDM: see file LEAD-2_programming_steps and output of "STEP 3 - BALANCE Assessment (with dummy outcome) - Paragraphs 9-10 of the protocol"

Date conducted: 06/16/2021

After review of initial feasibility and power analyses, complete creation of the remaining covariates from Section 6.2. Again, using the dummy outcome of a 90-day gap in database enrollment, complete a 1:1 PS-matched analysis. The PS should include the complete list of covariates.

• Provide plot of PS distributions stratified by treatment group.

Note- Please refer to Appendix B.

• Report covariate balance after matching.

Note- For Table 1, please refer to **Appendix B**.

• Report reasons for censoring by treatment group.

	Overall (n. 746)	Liraglutide – exposure (n. 373)	Glimepiride – comparator (n. 373)
Outcome (dummy)	0 (0%)	0 (0%)	0 (0%)
Death	0 (0%)	0 (0%)	0 (0%)
Start of an additional exposure	9 (1.2%)	6 (0.8%)	3 (0.4%)
End of index exposure	194 (26.0%)	137 (18.4%)	57 (7.6%)
Maximum follow-up time	340 (45.6%)	137 (18.4%)	203 (27.2 %)
End of patient data	5 (0.7%)	3 (0.4%)	2 (0.3%)
End of patient enrollment	61 (6.3%)	25 (3.4%)	36 (4.8%)
Start of additional antidiabetic drugs + Nursing home + Metformin discontinuation with allowed 60 days gap	137 (18.4%)	65 (8.7%)	72 (9.7%)

• Report follow-up time by treatment group.

Median Follow-Up Time (Days) [IQR]			
Patient Group	Overall (n. 746)	Liraglutide (n. 373)	Glimepiride (n. 373)
Overall Patient Population	188 [97 - 212]	150 [89 - 212]	212 [119 -212]

• Report overall mean (sd) of the primary outcome (from initial feasibility analysis).

	Optum CDM
Outcome – Lab value HbA1cmean (sd)	7.24 (1.01)

10. Final Power Assessment

Date conducted:

• Re-calculate power in the appropriate excel table, using the revised number of matched patients from the PS-match in Section 9. All other parameters in the table should be the same as in Section 8.

Non-inferiority Analysis	
Standard deviation of outcome	1.01
Non-inferiority limit	0.4
Alpha (2-sided)	0.05
Power (1-beta)	90%
Sample size required per group	110
Total sample size required	220
Number of patients matched	746
Reference	373
Exposed	373

• Stop analyses until balance and final power assessment are reviewed by primary investigators, FDA, and assigned members of advisory board.

Reviewed by PI:	[name]	Date reviewed:	07/16/2021
Reviewed by FDA:	[name]	Date reviewed:	08/2/2021
Reasons for stopping			
analysis (if required):			

11. Study Confidence and Concerns

Deadline for voting on study confidence and listing concerns:

Date votes and concerns are summarized:

- If final feasibility and power analyses are reviewed and approved, proceed to the remaining protocol steps.
- All study team and advisory board members that review this protocol should at this stage provide their level of confidence for the success of the RWD study in the Google Form. This form also provides space for reviewers to list any concerns that they feel may

contribute to a failure to replicate the findings of the RCT, including differences in study populations, poor measurement of study variables, or residual confounding. All responses will be kept confidential and individual-level results will only be shared with the individual respondent.

• After the deadline for voting has passed, provide the distribution of responses and summarize all concerns here.

12. Register study protocol on clinicalTrials.gov

Date conducted:

• Register the study on clinicalTrials.gov and upload this document.

13. Comparative Analyses

Aetion report name:

Date conducted:

- 13.1 For primary analysis:
- 13.2 For sensitivity analyses:

14. Requested Results

14.1 Table 1: Baseline characteristics before and after adjustment

Variable	Before adjustment		After adjustment			
	Referent	Exposure	Std. diff.	Referent	Exposure	Std. diff.
Number of patients			-			-
Age categories						

14.2 Table 2: Follow-up time

Patient Group	Median Follow-Up Time (Days) [IQR]
Overall Patient Population	
Referent	
Exposure	

14.3 Table 3: Censoring events

	Overall	Referent	Exposure
Outcome			
Death			
Start of an additional exposure			
End of index exposure			
Specified date reached			
End of patient data			
End of patient enrollment			

14.4 Table 4: Results from primary analyses;

Analysis	No. exposed events	No. referent events	Exposed rate	Referent rate	HR (95% CI)
Crude					
Analysis 1					
Analysis 2					

HR, Hazard Ratio; CI, Confidence Interval.

14.5 Table 5: Results from secondary analyses.

15. References

Julious SA. Sample sizes for clinical trials with Normal data. Statist. Med. 2004; 23:1921-1986. Sealed Envelope Ltd. 2012. Power calculator for continuous outcome non-inferiority trial. [Online] Available from: https://www.sealedenvelope.com/power/continuous-noninferior/ [Accessed Fri May 07, 2021].

#	LEAD-2 trial definitions	Implementation in routine care		for further details or any missing information: 618wrywYjEaXzfLTcuK-VCenb6b-gV?usp≕sharing
	Trial details - clini	ICD-10 codes are not listed in this document because of excel cell size limitations and excessive number of ICD-10 codes. Full ICD-10 code lists will be available in the above Google Drive Folder (link above). ICD-9 to ICD-10 code conversions were completed using a SAS macro that implements forward/backward mapping based on the CMS ICD-9 to ICD-10 mapping: https://www.nber.org/data/icd/9-icd-10-cm-and-nex-crosswalk-general-equivalence-mapping.html		
	EXPOSURI	E vs. COMPARISON	References/Rationale	Color coding
	Exposure: Liraglutide s.c. 0.6 mg/day, 1.2 mg/day and 1.8 mg/day in combination with metformin (1500-2000 mg/day) for 26 weeks Reference for non-inferiority: Glimepiride (4 mg/day) in combination with metformin (1500-2000 mg/day) Reference for superiority: Metformin monotherapy (1500-2000 mg/day) Aim: To evaluate whether the effect on glycaemic control (as measured by change in HbA1c) of treatment with 0.6 mg/day, 1.2 mg/day and 1.8 mg/day of liraglutide in combination with metformin was superior to metformin monotherapy and non-inferior to metformin and glimepiride combination therapy after 26 weeks of treatment.	Exposure: new-use of Liraglutide (washout 180 days) in combination with metformin NDC Generic Name: LIRAGLUTIDE NDC Brand name: Viktoza (FlexPen) Reference: new use of Glimepiride (washout 180 days) in combination with metformin NDC Generic Name: GLIMEPIRIDE NDC Brand name: GLIMEPIRIDE AMARYL		Criteria
	PRIMA	RY OUTCOME		Adequate mapping in claims
	Change in HbA1c from baseline to week 26 Note: in the trial missing values are replaced with last value carried forward [LVCF]	Measured as change in HbA1c from baseline to the last recorded HbA1c value between 56 and 212 days after drug initiation: Loinc codes: 17855-8, 17856-6, 41995-2, 43150-2, 4548-4, 4549-2, 55454-3, 71875-9, 74246-0		Intermediate mapping in claims
	INCLUS	SION CRITERIA		Poor mapping or cannot be measured in claims
0	Informed consent obtained before any trial-related activities (trial-related activities are any procedure that would not have been performed during normal management of the subject).	N/A		Can't be measured in claims but not important for the analysis
1	(1.1) Subjects diagnosed with type 2 diabetes and (1.2) treated with OAD(s) for at least three months.	1.1 Selecting patients with a diagnosis of type 2 diabetes measured from the time of enrollment to the day of drug initiation inpatient (any position), outpatient (any position): Type 2 diabetes: 1.1 Selecting patients with at least two prescriptions of metformin within 183 days before cohort entry (OADs treatment ≥ 3 months), and 1.3 Concomitant or current use of metformin at cohort entry date in both treatment groups: Generic name: Metformin Hel 1.4 Selecting patients with no other anti-diabetic treatments within the 180 days before cohort entry:		
2	HbA1c: -7.0-10.0% (both incl.) in subjects on OAD combination therapy -7.0-11.0% (both incl.) in subjects on OAD monotherapy.	2.1 Selecting patients with 3 measurements of HbA1c values (between 2-20%) recorded within 365 days prior to and including cohort entry: Loine codes: 17855-8, 17856-6, 41995-2, 43150-2, 4548-4, 4549-2, 55454-3, 71875-9, 74246-0 AND Result value 2-20% 2.2 Selecting patients with at least one measurement of HbA1c value (between and included 7-11%) recorded within the last 91 days prior to and including cohort entry: Loine codes: 17855-8, 17856-6, 41995-2, 43150-2, 4548-4, 4549-2, 55454-3, 71875-9, 74246-0 AND Result value 7-11%		
3	Age 18-80 years, both inclusive (as allowed according to local guidelines for metformin and glimepiride treatment). This inclusion criterion has been modified for Site 344 in Australia according to Substantial Protocol Amendment No. 1-AU, see Section 9.8.1.	Female and male, 18-80 years at the time of drug initiation		
	EXCLU]	

		Measured 180 days prior to and including the day of drug initiation inpatient (any position), outpatient (any position):	
1	Body mass index (BMI) >= 40.0 kg/m2.	Morbid obesity diagnosis or BMI >= 40 kg/m2: ICD 9 diagnosis: 278.01, 278.03, V85.4x ICD 10 diagnosis: E66.01, E66.2, Z68.4x	
		NB. Codes for bariatric surgey, complications of bariatric surgery and prescriptions of drugs for weight loss were not included in the measure since this exclusion criterion aims to exclude specifically patients with morbid obesity. Codes for obesity during pregnancy were not included because of the exclusion criterion #17.	
		Measured 180 days prior to and including the day of drug initiation:	
		NDC Generic Name:	
2	Treatment with insulin within the last three months prior to trial (except for short-term treatment due to intercurrent illness at the discretion of the investigator).	Please refer to Insulin in "Anti-diabetic treatments"	
		NB. Although the trial excluded patients in treatment with insulin within the 90 days before drug initiation, with real- world data we are required to be more conservative and to extend the washout period to 180 days. In fact, a 90-day washout applied in real world does not garantee the exclusion of prevalent users (i.e. patients on active insulin therapy) from the cohort.	
		Measured 180 days prior to and including the day of drug initiation in any diagnosis position and inpatient or outpatient care setting:	
